- Post dose vital signs assessment: Pulse rate is to be measured in a supine position after 5 minutes of rest pre-dose and at the time points of post-dose PK sampling until 110 mins post-dose (15-25 mins, 25-35 mins, 35-55 mins, 70-110 mins post-dose). Pulse rate should be taken before the respective blood for PK sampling is drawn. Systolic/diastolic blood pressure (including orthostatic measurement) is to be done at baseline and at 70-110 minutes post dose. This procedure is to be performed in a quiet environment and unexpected disturbances have to be avoided. In case of an unexpected disturbance (for example slamming door) this measurement may be repeated.
- Instruct patient NOT to take study medication on the morning of trial visits.

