**Proprietary confidential information.**

© 2017 Boehringer Ingelheim International GmbH or one or more of its affiliated companies. All rights reserved.

This document may not - in full or in part - be passed on, reproduced, published or otherwise used without prior written permission.

*Statistical analysis and reporting of adverse events will concentrate on treatment-emergent adverse events. To this end, all adverse events occurring between first drug intake and end of the residual effect period after last treatment administration will be considered 'treatment-emergent'.*

*Adverse events that start before first drug intake and deteriorate under treatment will also be considered as 'treatment-emergent'.*

*Frequency, severity, and causal relationship of adverse events will be tabulated by system organ class and preferred term after coding according to the current version of the Medical Dictionary for Drug Regulatory Activities (MedDRA).*

Descriptive statistics of laboratory values over time and for the difference from baseline will be provided. Frequency tables of changes with respect to the reference range between baseline and last value on treatment will also be presented.

[figure not shown]
*Vital signs, ECG and other safety parameters at screening/run-in/baseline, during the course of the trial and at the end-of-trial evaluation will be assessed with regard to possible changes compared to findings before start of treatment.*

*The responses to the C-SSRS will be summarized through descriptive statistics.*

*More details of these analyses will be included in the TSAP.*

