6.7 BASELINE, TIME WINDOWS, AND CALCULATED VISITS

For efficacy, the baseline is defined as the pre-treatment observation at Visit 3. All other baseline variables will be observed from Visit 1.

For laboratory safety measurements, the last values prior to study drug administration will be considered as baseline values.

The midpoint between two on-treatment visits defines the end of a time window, with the midpoint being included in the time window of the preceding visit.

Table 6.7: 1 Time windows for all pre/on-treatment safety visits

Visit number	Visit label	Planned days	Interval (actual days on treatment)
1	Screening	-28	$(-\infty, \text{PBORI}-1]$
2	Placebo Run-in period	-14	$[\text{PBORI}, \text{TREATMENT}-1]$
3	Baseline	1	$[\text{NA}, 1]$
4a	Week 1	8	$[2, 11]$
4b	Week 2	15	$[12, 18]$
4c	Week 3	22	$[19, 25]$
5	Week 4	29	$[26, 43]$
6	Week 8	57	$[44, 73]$
EOT	Week 12	85	$[74, 99]$
FU	Follow-up	113	$[100, \text{Study drug stop date} + 7 \text{ days}]$

These time windows are defined based on the planned number of days after the date of first administration of study drug. Reasons to base the time windows on the actual treatment start date rather than the randomisation date are:

- If first intake of study drug shows a large delay by e.g. more than one week after the date of randomisation, a measurement taken four weeks after randomisation rather reflects the drug effect after three weeks than after four weeks and thus may underestimate the treatment effect at this visit.

Proprietary confidential information © 2017 Boehringer Ingelheim International GmbH or one or more of its affiliated companies

- With large delays of the introduction of study drug after the randomisation, the time window for the first on-treatment visit could include times the patient was not yet on study drug.

Table 6.7: 2 Time windows for on-treatment efficacy measurement scheduled for each on treatment visit

Visit Number	Visit label	Planned days	Time window (actual days on treatment)	
			Start	End ^A
3	Baseline	1	NA	1 ^B
5	Week 4	29	2	57
EOT	Week 12	85	58	Study drug stop date + 7 days

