A In case of premature discontinuation of the study drug an EOT Visit has to be performed. If such an EOT Visit falls into the time window of a previous visit, measurements will be assigned to this previous visit and the visit value will be determined as described below. In this case the time window for the visit that includes EOT Visit will end 7 days after the study drug stop date, including Day 7.

B Only values taken prior to the start of treatment with randomised study drug can be considered baseline values. Time windows will be used for assignment of measurements to scheduled visits.

Repeated and unscheduled efficacy and safety measurements will be

assigned to the nominal visits and listed in the subject data listing (SDL) according to the time windows described above.

If there are several safety laboratory values in one time window on treatment, the worst of these will be selected for the by-visit analyses.

For efficacy measurements, only one observation per time window will be selected for analysis at an on-treatment visit – the value will be selected which is closest to the protocol planned visit day. If there are two observations which have the same difference in days to the planned day or if there are two observations on the same day, the first value will be used. If an observation is available on the last day of treatment, this observation will be preferably selected over any later observation that is still within the time window.

Note: for LOCF imputation, the last observed on-treatment value will be carried forward, whether or not it was selected in the previous time window. For more details on LOCF refer to [section 6.6](#).

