7.8.3 Vital signs

Only descriptive statistics are planned for this section of the report.

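### The only scheduled post-dose pulse and blood-pressure readings have no on-treatment time point in the SAP's safety windows

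*SAP*

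**What the plan says.** - **SAP 6.7, Table 6.7:1** ("Time windows for all pre/on-treatment safety visits"): Visit 3, labelled Baseline, runs up to and including Day 1. Visit 4a (Week 1) covers Days 2 to 11. No clock time or footnote is given.
- **SAP 6.7, Table 6.7:2** (efficacy): the baseline window also ends on Day 1, but that entry carries footnote B: "Only values taken prior to the start of treatment with randomised study drug can be considered baseline values".
- **SAP 6.7, other baselines**: "For laboratory safety measurements, the last values prior to study drug administration will be considered as baseline values". A further sentence takes all other baseline variables from Visit 1. SAP 7.8.4 sets a baseline before first intake for ECG findings.
- **SAP 7.8.3, Vital signs**, consists of one sentence: "Only descriptive statistics are planned for this section of the report".
- **SAP 7.8** refers the safety analysis to protocol 7.3.3, where vital signs "will be assessed with regard to possible changes compared to findings before start of treatment".
- **SAP 6.1, Table 6.1:2** starts the Treatment interval at the date and time of first administration of study drug.
- **Protocol 6.2.2, Visit 3**: pulse is measured before the dose and "at the time points of post-dose PK sampling until 110 mins post-dose (15-25 mins, 25-35 mins, 35-55 mins, 70-110 mins post-dose". Blood pressure is taken at baseline and at 70-110 minutes. Protocol 5.2.5.2 requires these extra readings at Visit 3 only; the investigator may repeat the pulse procedure at another visit if clinically necessary.

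**The concern.** A rise in pulse is a cardiac effect that the protocol itself describes. Section 1.2 (Clinical safety) reports a concentration-dependent increase that is greatest at about 20-30 minutes after dosing and then disappears quickly. An effect of that shape is seen only in readings taken soon after a dose, and the trial schedules such readings once, on Day 1.

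If the vital-sign tables are programmed from Table 6.7:1, those readings take the Baseline label or drop out of the by-visit on-treatment display. The report could then show little pulse change at Weeks 1 to 12 in every arm and never summarise the readings made to detect the effect. The SAP also leaves the vital-sign baseline open, so two programmers could reasonably choose different values.

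**Working it through.** No power or alpha figure is involved. The check is a comparison of passages, a recalculation of the windows and a count.

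**1. Reproduce the windows.** The SAP's rule, cut before its final word, is "The midpoint between two on-treatment visits defines the end of a time window, with the midpoint being included in the time window of the preceding". With the planned days in Table 6.7:1, window end = floor((day of this visit + day of next visit) / 2):

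| Visit | Calculation | Result | Table |
|---|---|---|---|
| 4a | (8+15)/2 = 11.5 | 11 | 11 |
| 4b | (15+22)/2 = 18.5 | 18 | 18 |
| 4c | (22+29)/2 = 25.5 | 25 | 25 |
| 5 | (29+57)/2 = 43 | 43 | 43 |
| 6 | (57+85)/2 = 71 | 71 | 73 |
| EOT | (85+113)/2 = 99 | 99 | 99 |

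The Week 8 end differs by two days, which is a separate discrepancy. The Day 1/Day 2 boundary is not a midpoint, since (1+8)/2 = 4.5. It is set by the table alone, so the midpoint rule gives no help with Day 1.

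**2. Place the Day 1 readings.** Windows are counted from first administration, which takes place at Visit 3.

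| Reading | Relative to dose | Table 6.7:1 window | Table 6.1:2 interval |
|---|---|---|---|
| Pulse | before | Baseline | before Treatment |
| Pulse 15-25 min | after | Baseline | Treatment |
| Pulse 25-35 min | after | Baseline | Treatment |
| Pulse 35-55 min | after | Baseline | Treatment |
| Pulse 70-110 min | after | Baseline | Treatment |
| Blood pressure | before | Baseline | before Treatment |
| Blood pressure 70-110 min | after | Baseline | Treatment |

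Post-dose readings are 4 of 5 for pulse and 1 of 2 for blood pressure. None falls in the Day 2-11 window or later. The two SAP tables therefore classify the same readings differently.

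**3. Ask whether later visits replace them.** Protocol 6.1 tells patients to withhold the morning dose before clinic visits. Protocol 4.1.4 places the dose after blood sampling, and 6.2.2 places blood pressure before it. Vital signs at Visits 5 and 6 are thus essentially pre-dose, and no drug is taken at EOT. At Visit 4a the visible flow chart shows no blood sample, so the order within that visit is less firmly fixed, but no timed post-dose reading is scheduled.

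**4. Compare the rules by data type.**

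| Data | Pre-dose baseline stated in SAP | Rule for several values in one window |
|---|---|---|
| Efficacy | yes (footnote B) | closest to planned day, else first |
| Laboratory | yes | worst value |
| ECG | yes (7.8.4) | none stated |
| Vital signs | no; only the general Visit 1 sentence | none stated |

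Vital signs are the one type here with scheduled post-dose readings on Day 1, and the one type without its own pre-dose rule in the SAP.

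**5. Size.** The documents do not say how several Day 1 vital-sign readings would be selected or combined. No numerical bias follows from them.

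**The case against.** A reader might infer something stronger: that the SAP counts the Day 1 post-dose readings as baseline values, contradicts the protocol, and so hides a rise of up to 7-13 bpm in later comparisons. The documents do not support this.

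- A visit label is not a baseline value. Table 6.7:1 assigns readings to visits, and no rule averages the Day 1 vital signs or selects a post-dose one as baseline.
- SAP 7.8 adopts protocol 7.3.3, which compares with findings before treatment. Flow chart footnote 3 and section 3.3.4.1 define the vital-sign baseline as pre-dose, and 6.2.2 separates the baseline blood pressure from the 70-110 minute one.
- Read literally, the Visit 1 sentence in SAP 6.7 would put the baseline at screening, where Day 1 readings could not affect it.
- The 7-13 bpm figure is a median maximum in CYP2C19 poor metabolizers at 100 mg, above every dose in this trial. At essentially pre-dose later visits, little of such a rise would remain to be hidden.

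It is also fair to say that the safety signal has other routes. The withdrawal criteria in 3.3.4.1 act on these readings at once, clinically relevant changes become adverse events, and SAP Table 6.2:1 item E2 flags a failure to discontinue for heart-rate elevation. Parts of the SAP and the pharmacokinetic material are redacted, so what can be said about absence is limited to the visible text.

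These points dispose of the contamination argument. They do not give the readings an analysis. Deferring to 7.3.3 settles the comparator but creates no post-dose time point. Adverse-event reporting depends on the investigator's judgement of relevance, and item E2 counts only failures to discontinue. Section 7.8.3 is visible and names no Day 1 summary, although protocol 7.3.3 left further detail to the SAP.

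**Conclusion.** The point holds as a gap in the SAP. Table 6.7:1 has no pre-dose restriction, and all five scheduled post-dose vital-sign time points (four pulse, one blood pressure) have no on-treatment place in the by-visit windows, although Table 6.1:2 already puts them in the Treatment interval. By-visit on-treatment summaries built as written would hold essentially pre-dose clinic readings and can miss a short-lived pulse effect. The Visit 1 sentence in SAP 6.7 also needs reconciling with the protocol's pre-dose Visit 3 baseline.

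No contaminated baseline is shown and no bias can be quantified. The conclusion assumes that the windows are applied by calendar day as written, that the visit order in protocol 4.1.4, 6.1 and 6.2.2 is followed, and that no redacted section supplies the missing summary. It merits correction because the remedy is cheap and concerns the readings scheduled to show this effect.

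**What to change.** 1. In Table 6.7:1, apply footnote B to the Day 1 entry, or split Day 1 at the time of the first randomised dose so that later readings that day are on-treatment.
2. State in SAP 6.7 or 7.8.3 that the vital-sign baseline is the protocol's pre-dose Visit 3 value, and reconcile this with the sentence that takes other baseline variables from Visit 1.
3. In SAP 7.8.3, tabulate by arm the change from pre-dose at each Day 1 time point: pulse at 15-25, 25-35, 35-55 and 70-110 minutes, and blood pressure at 70-110 minutes. Add descriptive counts of patients meeting the pulse criteria already stated in protocol 3.3.4.1.

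No clinical rule changes. The cost is a few lines of SAP text and one extra descriptive table from data already collected. Item E2 is marked as an automatic check, so some programming of heart-rate elevation is needed in any case.

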7 PLANNED ANALYSIS

For End-Of-Text (EoT) tables, the set of summary statistics is: N / Mean / SD / Min / Median / Max. For tables that are provided for endpoints with some extreme data, median, quartiles and percentiles should be preferred to mean, standard deviation, minimum and maximum.

Tabulations of frequencies for categorical data will include all possible categories and will display the number of observations in a category as well as the percentage (%) relative to the respective treatment group (unless otherwise specified, all patients in the respective patient set whether they have non-missing values or not). Percentages will be rounded to one decimal place. The category missing will be displayed only if there are actually missing values.

7.1 DEMOGRAPHICS AND OTHER BASELINE CHARACTERISTICS

Only descriptive statistics are planned for this section of the report.

7.2 CONCOMITANT DISEASES AND MEDICATION

Only descriptive statistics are planned for this section of the report.

A summary of concomitant diseases will be provided by treatment group, System Organ Class (SOC) and Preferred Term (PT).

7.3 TREATMENT COMPLIANCE

Only descriptive statistics are planned for this section of the report.

Overall compliance will be calculated as mentioned in CTP section 4.3

7.4 PRIMARY ENDPOINT(S)

The primary analysis is at 12 weeks and will be performed on the full analysis set (FAS).

Figures and tables will be displayed for the MMRM analysis results over time.

Assignment to stratum will be based on IRT and eCRF data.

7.4.1 Primary efficacy analysis

The primary analysis and hypothesis testing are described in section 7.3.1 of the CTP.

Proprietary confidential information © 2017 Boehringer Ingelheim International GmbH or one or more of its affiliated companies

7.5 SECONDARY ENDPOINTS

Figures and tables will be displayed for the MMRM and ANCOVA analyses results over time.

7.5.1 Key secondary endpoint

This section is not applicable as no key secondary endpoint has been specified in the protocol.

7.5.2 Secondary endpoints

The same primary analysis model will be performed for the secondary endpoint CDR-SB.

The secondary endpoints ADAS-Cog11 and ADCS-ADL will use the following model:

ANCOVA:

[figure not shown]
Analysis of covariance will be used for the change from baseline secondary endpoint score after 12 weeks of treatment; terms include baseline value for the secondary endpoint measure, treatment and stratification factor current AChE-I use.

[REDACTED]

[REDACTED]

[REDACTED]

[REDACTED]

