## CLINICAL TRIAL PROTOCOL SYNOPSIS

Name of company: Boehringer Ingelheim		Tabulated Trial Protocol	
Name of finished product: NA			
Name of active ingredient: BI 409306			
Protocol date: 17 Oct 2014	Trial number: 1289.7		Revision date: 23 Feb 2017
Title of trial:	A multi-centre, double-blind, parallel-group, randomised controlled study to investigate efficacy, safety and tolerability of orally administered BI 409306 during a 12-week treatment period compared to placebo in patients with cognitive impairment due to Alzheimer's Disease		
Co-ordinating Investigator:	[REDACTED]		
	Phone: [REDACTED] Fax: [REDACTED]		
Trial site(s):	60		
Clinical phase:	II		
Objective(s):	To assess safety, tolerability and efficacy of different doses of BI 409306 compared to placebo in treatment of cognitive impairment due to AD		
Methodology:	Placebo -controlled, double-blind, randomised parallel-design comparison of 5 groups over 12 weeks of treatment.		
No. of patients:	total entered: 354 each treatment: 118 for placebo group and 59 for each treatment group		
Diagnosis :	Patients with diagnosis of mild Alzheimer's dementia according to the recommendations from the National Institute on Aging-Alzheimer's Association workgroups on diagnostic guidelines for Alzheimer's disease and ICD10 and DSM V criteria		
Main criteria for inclusion:	The population will include male and female patients at least 55 years old with mild Alzheimer's dementia. A MMSE (Mini-Mental-State-Examination) score between 18-26, an ADAS-cog 11 score higher than 12 at screening, and a global CDR score of 1 or greater are required for inclusion. A caregiver has to be available for study site activities and on call by arrangement with the study site.		
Test product(s):	BI 409306		
dose:	10mg QD, 25mg QD, 50mg QD, 25mg BID		
mode of admin.:	Tablet, Oral		

Proprietary confidential information.

© 2017 Boehringer Ingelheim International GmbH or one or more of its affiliated companies. All rights reserved.

This document may not - in full or in part - be passed on, reproduced, published or otherwise used without prior written permission.

Name of company: Boehringer Ingelheim		Tabulated Trial Protocol	
Name of finished product: NA			
Name of active ingredient: BI 409306			

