## FLOW CHART

Trial Period	Screening	Placebo Run-in Period	Treatment Period							Follow-up
			3 Baseline	4a 	4b 	4c 	5	6	EOT/ED 	
Visit	1	2		1	2	3	4	8	12	16
Studyweeks	-3	-2		1	2	3	4	8	12	16
Study-Day (or duration during screening/ run-in)	Duration 1-7 days	Duration at least 14 and at most 21 days after screening period	1	8	15	22	29	57	85	EOT +28
Visit window (in days)				±1	±1	±1	±3	±3	+3	±3
Patient information & informed consent signed ████████████████████	X									
Register Patient in IRT	X									
Randomisation (via IRT)			X							
Demographics	X									
Medical history / baseline conditions	X									
In-/exclusion criteria	X	X	X							
Imaging of the Brain 	X									
Concomitant medications	X	X	X	X	X	X	X	X	X	X
Height (screening only)/weight	X								X	X
Vital signs	X		X	X	X 	X 	X	X	X	X
Post Dose Heart Rate Procedure 			X							
Physical examination	X								X	
Neurological examination	X								X	
Resting ECG (digital)	X		X	X	X 	X 	X	X	X	X
Adverse events	X	X	X	X	X 	X 	X	X	X	X
Dispense trial medication 		X	X				X	X		
Collect study drug			X				X	X	X	
Medication Compliance Check			X				X	X	X	
Laboratory tests: Chemistry, haematology, urinalysis	X		X				X	X	X	X
Blood Glucose (Onsite) 	X		X				X		X	
████████████████████			█					█		
████████████████████			█						█	
Urine drug screen	X								X	
Urine pregnancy test 	X		X				X	X	X	
Vitamin B12 and folate	X								X	
RPR (FTA, if RPR positive)	X									
Prospective Suicidality Monitoring										
C-SSRS	X 	X 	X 	X 	X 	X 	X 	X 	X 	X 

Proprietary confidential information.

© 2017 Boehringer Ingelheim International GmbH or one or more of its affiliated companies. All rights reserved.

This document may not - in full or in part - be passed on, reproduced, published or otherwise used without prior written permission.

Trial Period	Screening	Placebo Run-in Period	Treatment Period							Follow-up
			3 Baseline	4a 	4b 	4c 	5	6	EOT/ED 	
Visit	1	2								FU
Studyweeks	-3	-2		1	2	3	4	8	12	16

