### 3.3.2 Inclusion criteria

Patients are included in this study if they meet all of the following criteria:

1. Diagnosis of mild Alzheimer's Dementia according to the recommendations from the National Institute on Aging-Alzheimer's Association workgroups on diagnostic guidelines for Alzheimer's disease (see [section 3.3.1](#)).
2. Mini-Mental State Examination (MMSE) score of 18-26, an Alzheimer's Disease Assessment Scale – cognitive subscale (ADAS-cog11) score > 12 and a global CDR score of 1 or greater at screening.
3. Patients must have given written informed consent in accordance with GCP and local legislation prior to any study procedures. All patients must be able to give informed consent personally and have capacity for such consent. An informed consent given by a legal representative will not be accepted.
4. Patients must have a reliable study partner (per investigator judgement for instance a family member, partner etc., guardian (must be always the same person)) who is in close contact with the patient, available on call and who is able to contribute to the assessment of the ratings of the functional endpoints including CDR-SB at specific study visits as stated in the [flow chart](#). This person will be able to communicate in the language in which the patient is being assessed and should also serve as a backup contact for the study site. The study partner must sign a separate informed consent form which describes their contributions during the study.
5. Patients must have at least 6 years of formal education and fluency in the test language as verbally confirmed by the patient and documented by the study investigator.
6. Previous use of AD medications (AChEIs, memantine) is allowed up 3 month prior to screening. Patients who are currently taking AChEIs are eligible as long as they have been using a stable dose for at least 3 months prior to screening and no change is foreseen for the duration of the study. This dose must be consistent with the product label in the concerned country. Patients currently taking memantine are excluded. .
7. Male or female patients at least 55 years of age. Patients older than 85 years may be included based on an acceptable general health status, (e.g. concomitant diseases, physical capability to follow the required study procedures [visits etc.]) at discretion of the investigator.

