## 6.2.2 Treatment period(s)

### Visit 3

Visit 3 is the baseline/randomisation visit and marks the beginning of the treatment period. The neuropsychological assessments may be done on the day before the randomisation visit (last day of the screening period) if agreed between site staff and patient. In any case it needs to be ensured that the recommendations for the conduct of the neuropsychological assessments (refer to [section 6.2](#) for details) are followed.

- Study procedures have to be completed according to the [Flow Chart](#).
- Collect returned run-in medication.
- Re-assessment of in/exclusion criteria including assessment of compliance of study drug intake.
- Neuropsychological assessments and collection of urine and blood for laboratory testing must be performed prior to administration of study medication.
- Blood pressure must always be measured before taking any blood sample.
- ECG will be performed
- Laboratory samples will be collected as described in [Flow Chart](#).

Proprietary confidential information.

© 2017 Boehringer Ingelheim International GmbH or one or more of its affiliated companies. All rights reserved.

This document may not - in full or in part - be passed on, reproduced, published or otherwise used without prior written permission.

- For diabetic patients with anti-diabetic therapy: exclusion of hypoglycemia for the period of the neuropsychological assessment (documented plasma glucose concentration  $\geq 90$  mg/dl (5mmol/l) at the beginning and directly after the assessment).
- Administer the following neuropsychological assessments in the following order:
  - CDR-SB
  - NTB
  - ADCS-ADL
  - ADAS-cog11
- Administration of C-SSRS (baseline since last visit scale)
- The intake of trial medication and handling of medication blisters should be discussed and (if deemed necessary) re-trained with the patient and the caregiver. The dose of trial medication should be taken by the patient after the neuropsychological assessments have been administered.
- Contact IRT to randomise patient and obtain medication kit numbers and dispense the medication to the patient (if neuropsychological testing was not performed according to the protocol patients should not be randomized, please refer to [inclusion criteria](#), #6).
- 

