### Visits 5, 6 and EOT/ED

- Study procedures have to be completed according to the [Flow Chart](#).
- Collect returned medication at every visit prior to dispensing new medication
- Neuropsychological assessments and collection of urine and blood for laboratory testing [REDACTED] must be performed prior to administration of study medication
- For diabetic patients with antidiabetic therapy: exclusion of hypoglycemia for the period of the neuropsychological assessment (documented plasma glucose concentration  $\geq 90$  mg/dl (5mmol/l) at the beginning and directly after the assessment).
- Administer the following neuropsychological assessments in the following order:
  - CDR-SB (V5 and EOT)
  - NTB (V5 and EOT)
  - ADCS-ADL (EOT)
  - ADAS-cog11 (EOT)
- Administration of C-SSRS (baseline since last visit scale)
- The intake of trial medication and handling of medication blisters should be discussed and (if deemed necessary) re-trained with the patient and the caregiver. The dose of trial medication should be taken by the patient after the neuropsychological assessments have been administered.
- [REDACTED]
- Blood pressure must always be measured before taking any blood sample
- Laboratory samples will be collected as described in [Flow chart](#).
- New medication kit must be dispensed at Visits 5 and Visit 6 and IRT must be contacted at those visits to obtain medication kit numbers to be dispensed.
- Instruct patient NOT to take study medication on the morning of next trial visits.
- Visit EOT/ED is the end of treatment visit. Study medication will not be taken at Visit EOT/ED.

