9.3 SAS CODE

The below table summarises the SAS code for the main analyses

Table 9.3.1 SAS Code for main analyses

Analysis	Code	Comments
Dose response	Test the following model: $\mu(d_i) = \beta_0 + \beta_1 d_i + \beta_2 d_i^2$ PROC GLM DATA=one; MODEL chgept = trt trt*trt; RUN; Treat BID dose as an in between dose = (QD + 2*QD)/2	Dose is treated as a continuous variable. $\mu(d_i)$ denotes the mean response of dose level i.
MMRM	PROC MIXED DATA=dat cl method=reml ORDER=formatted; CLASS trt visit patient <AChEI>; MODEL chgept = trt baseline visit trt*visit baseline*visit <AChEI> / ddfm=KR solution; REPEATED visit / type=un subject=patient r rcorr ; LSMEANS trt*visit / pdiff=all cl; RUN ;	current AChEI use for 1289.7
ANCOVA	PROC MIXED data=one METHOD=reml ORDER=formatted; CLASS trt ; MODEL chgept = baseline trt <AChEI>; LSMEANS trt / CL DIFF OM ; RUN;	current AChEI use for 1289.7

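### Optional gain for a descriptive secondary endpoint: ADAS-cog11 is measured twice before treatment, but its ANCOVA adjusts only for the Visit 3 value

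*SAP*

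**What the plan says.** **Visit 1.** The protocol synopsis requires an ADAS-cog11 "score higher than 12 at screening", and inclusion criterion 2 (Protocol 3.3.2) repeats this. The scale is in the flow chart and in the Visit 1 list in Protocol 6.2.1. Every eligible randomised patient should therefore have this score.

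**Visit 3.** ADAS-cog11 is in the Visit 3 list, and Protocol 6.2.2 says: "Neuropsychological assessments and collection of urine and blood for laboratory testing must be performed prior to administration of study medication". This is a second pre-treatment value.

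**After baseline.** The flow chart and Protocol 6.2.2 schedule ADAS-cog11 only at EOT. Amendment 2 removed it from Visit 5.

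**Interval between the two pre-treatment scores.** The screening period lasts 1 to 7 days, or up to 21 days if imaging is delayed. For the run-in the flow chart gives "Duration at least 14 and at most 21 days after screening period".

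**Analysis.** SAP 6.7: "For efficacy, the baseline is defined as the pre-treatment observation at Visit 3". SAP 7.5.2 gives the ANCOVA terms for ADAS-cog11 and ADCS-ADL: "terms include baseline value for the secondary endpoint measure, treatment and stratification factor current AChE-I use". The code in SAP 9.3 agrees: "MODEL chgept = baseline trt <AChEI>".

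**Status.** Protocol 7.2 makes all secondary p-values descriptive. Protocol 7.3.2 asks for adjusted means and contrasts with 95% confidence intervals.

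**The concern.** A single ADAS-cog11 score carries measurement error, so Visit 3 alone is an imperfect guide to a patient's level before treatment. An earlier score on the same scale is a natural second covariate, because it can supply part of what Visit 3 misses. With one scheduled post-baseline visit, a repeated-measures model has no intermediate value to draw on, so baseline covariates are the main remaining source of precision.

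What is at stake is the width of the ADAS-cog11 confidence intervals. Neither the primary NTB analysis nor the validity of the planned ANCOVA is in question.

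**Working it through.** **No plan figure to reproduce for this endpoint.** The only sample-size statement, Protocol 7.6, concerns NTB: effect size 0.45, 80% power, two-sided alpha 0.05, 59 per active arm and 118 on placebo, 354 in total. A two-sample t-test with unequal groups returns exactly 59/118/354, with power 80.1%. The documents give no effect size, variance, power or correlation for ADAS-cog11, so the correlations below are assumptions.

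**Formula.** Let a be the correlation between Visit 1 and Visit 3, b between Visit 3 and EOT, and c between Visit 1 and EOT. With Visit 3 in the model, change and raw EOT score have the same residual variance. As a share of total EOT variance it is:

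- Visit 3 only: 1 − b²
- both scores: 1 − (b² + c² − 2abc)/(1 − a²)

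The ratio of the second to the first is 1 − (c − ab)²/[(1 − a²)(1 − b²)]. With all three correlations equal to ρ it becomes (1 + 2ρ)/(1 + ρ)².

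**Results.** The confidence interval width scales with the square root of the ratio.

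| Assumption (a / b / c) | Calculation | Ratio | Variance reduction | Interval narrower by |
|---|---|---|---|---|
| all 0.5 | 2.0/2.25 | 0.889 | 11% | 6% |
| all 0.7 | 2.4/2.89 | 0.830 | 17% | 9% |
| all 0.8 | 2.6/3.24 | 0.802 | 20% | 10% |
| all 0.9 | 2.8/3.61 | 0.776 | 22% | 12% |
| 0.85 / 0.80 / 0.78 | 1 − 0.0100/0.0999 | 0.900 | 10% | 5% |
| 0.80 / 0.75 / 0.70 | 1 − 0.0100/0.1575 | 0.937 | 6% | 3% |
| 0.85 / 0.80 / 0.75 | 1 − 0.0049/0.0999 | 0.951 | 5% | 2% |
| 0.90 / 0.85 / 0.80 | 1 − 0.001225/0.052725 | 0.977 | 2% | 1% |
| 0.85 / 0.80 / 0.68 | c = ab, so 1 − 0 | 1.000 | 0% | 0% |

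The last row is the case where Visit 1 says nothing about EOT once Visit 3 is known.

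**Effect of the entry cut-off.** Requiring a Visit 1 score above 12 narrows its spread and trims the gain. In simulation with assumed SD 8, mean 16 to 24 and equal correlations of 0.6 to 0.8, the reduction was 9% to 18%. In simulated trials of 59 against 118 patients (assumed mean 20, SD 7, cut-off applied, true difference −2.0), the estimates with the added covariate averaged −2.00 and −1.99, so no bias appeared.

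**Effect of carrying baseline forward.** Under SAP 6.6.1, if more than 5% of data are missing, ANCOVA endpoints use LOCF, with baseline carried forward when no post-baseline value exists. Those patients have a change of zero, which Visit 1 cannot explain. With assumed mean 20, SD 7 and the cut-off applied:

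| a / b / c | None carried forward | 10% (assumed) | 20% (assumed) |
|---|---|---|---|
| all 0.8 | 17% | 15% | 14% |
| 0.85 / 0.80 / 0.75 | 4% | 4% | 3% |

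**Cost in degrees of freedom.** With 354 patients, the stated ANCOVA uses 7 parameters (intercept, four treatment terms, baseline, AChEI use), leaving 347. The extra covariate leaves 346. In the zero-gain case that inflates variance by a factor of about 347/346 = 1.003.

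**The case against.** The strongest reply is that nothing here is an error. Adjusting for the Visit 3 value and the stratification factor is a complete, pre-specified model. It follows Protocol 7.3.2, which asks for an ANCOVA resembling the primary model. That stands: this is an improvement to offer, not a defect to correct.

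Other points also stand in whole or part:

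- **Size.** A reduction of 17% to 22% requires Visit 1 and Visit 3 to be equally informative about Week 12. Visit 1 lies further from EOT, and Protocol 3.2 describes the run-in partly as time to become familiar with the test setting. Both make decaying correlation plausible.
- **Power.** A reader might infer that 80% power would rise to 82–88% with 5–20% less variance. The documents do not support this, because the 80% in Protocol 7.6 belongs to NTB and no power is stated for ADAS-cog11.
- **CDR-SB.** A reader might extend the idea to CDR-SB. The flow chart lists the screening CDR separately from CDR-SB, and nothing visible shows that a Visit 1 sum of boxes will be available for analysis.
- **Missing Visit 1 totals.** SAP 6.6.1 leaves the total missing when more than three items are missing. PROC MIXED would drop such a patient from the enlarged model, so a rule is needed. Cases should be few, since the score decides eligibility.
- **Redaction.** Text after the ANCOVA paragraph is blacked out, and the SAP contents list a section 7.5.3 on sensitivity analyses of secondary endpoints that is not visible. A further covariate analysis there cannot be excluded. The stated main model and its code are nonetheless clear.

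**Conclusion.** The point holds as an optional, nearly free improvement to one descriptive secondary analysis. The documents establish two pre-treatment ADAS-cog11 scores and a stated ANCOVA that uses one. Because the Visit 1 score precedes randomisation and the cut-off applies to all arms alike, adding it does not bias the treatment comparison.

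The gain cannot be fixed from the documents. Under the assumed correlations it lies between 0 and about 20% of residual variance (22% at the extreme, with all correlations at 0.9). It is probably in single digits if correlation decays, and slightly lower where baseline is carried forward. The matching narrowing of the confidence interval is 0 to about 10%. It would be a mistake to read this as showing that the planned analysis is biased or invalid, or that the trial's power or sample size is affected.

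**What to change.** Before unblinding, revise SAP 7.5.2 and 9.3 for ADAS-cog11 only:

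- Add the Visit 1 ADAS-cog11 total as a second continuous covariate: `MODEL chgept = baseline screening trt <AChEI>`.
- Keep change from Visit 3 as the endpoint, so SAP 6.7 is unchanged. Do not replace the baseline by the mean of the two scores, which would bring into it the score on which patients were selected.
- State a rule for a missing Visit 1 total that does not use treatment, such as the overall mean, so that no patient leaves the analysis.

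Leave the ADCS-ADL ANCOVA as it is, since that scale has no screening assessment. The change needs no new data and no extra patient burden. It costs one covariate in one statement, one sentence on missing values and one residual degree of freedom.
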